Analysis of Day 181 humoral and mucosal immunogenicity data may be performed and released as the data are available from the research laboratories. Any such analyses would be considered the final analysis for the endpoint, and included in the CSR.

Once the last subject completes the last visit, the final clinical database will be cleaned, monitored and locked. Unblinded analyses of safety, reactogenicity, colonization, and available immunogenicity data will then be performed by the DCC and will be included in the CSR. All safety analyses will be performed using the safety population, all immunogenicity analyses will be performed using the immunogenicity and the per-protocol (PP) populations, whereas all

colonization data will be summarized using per-protocol population. The analysis populations are defined below ([Section 11.4.1.](#))

All analyses will be presented by treatment group (i.e. group by BPZE1 10^9 CFU, BPZE1 10^7 CFU, or Placebo). In addition, results for BPZE1 at dose of 10^9 CFU will be further grouped by vaccination device (group by VaxINator or needleless tuberculin syringe) to allow for comparison of immunogenicity results with previous results from Phase 1 clinical trials of BPZE1 (these previous trials used needleless tuberculin syringe as device for administration).

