11.4.2 Safety Data

Summaries and analysis of safety data will be presented for the Safety Analysis Population. All summaries and analyses will be presented by treatment group.

Solicited AEs will be summarized by severity for each day after the study vaccination (Days 1-14 post study vaccination) and as the maximum severity over all 15 days. Additionally, solicited AEs will be analyzed by taking the most severe response over the follow-up period, dichotomizing into a binary variable (none versus mild, moderate, or severe) and using standard techniques, such as exact confidence intervals, to summarize the proportion of subjects reporting each symptom, any local symptom, and any systemic symptom. Summaries of solicited AEs will be presented separately for each study vaccination as well as overall study vaccinations by treatment arm. The proportion of subjects reporting symptoms may be compared between treatment arms using Chi-square or Fisher's exact test.

Unsolicited AEs will be coded by Medical Dictionary for Regulatory Activities (MedDRA[®]) for preferred term and system organ class (SOC). SAEs will be reported by detailed listings showing the event description, MedDRA[®] preferred term and SOC, relevant dates (study vaccinations and AEs), severity, relatedness, and outcome for each event. Non-serious unsolicited AEs will be summarized as number and percentage of subjects reporting at least one event in each MedDRA[®] preferred term and SOC, cross tabulated by severity and relationship to study product. Additionally, the proportion of subjects and exact 95% confidence intervals of AEs in aggregate and by MedDRA[®] categories will be computed.

Subjects will be tested for *B. pertussis* colonization by culture at Day 29 and, if positive, again at Day 46. The proportion of subjects with positive *B. pertussis* culture will be reported for the PP population at each time point with corresponding 95% confidence intervals.

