6. GENERAL STATISTICAL CONSIDERATIONS

6.1. General Principles

Unless otherwise noted, all continuous variables will be summarized using the following descriptive statistics: n (non-missing sample size), mean, standard deviation, median, maximum and minimum. The frequency and percentages (based on the non-missing sample size) of observed levels will be reported for all categorical measures. In general, all data will be listed, sorted by treatment group and subject, and when appropriate by visit number within subject. All summary tables will be structured with a column for each treatment in the order (BPZE1 10⁷ CFU administered via VaxINator, BPZE1 10⁹ CFU administered via VaxINator, BPZE1 10⁹ CFU administered via needleless tuberculin syringe, placebo administered via VaxINator) and will be annotated with the total population size relevant to that table/treatment, including any missing observations.

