9. SAFETY EVALUATION

All summaries and analysis of safety data will be presented for the Safety Analysis Population. Safety summaries will be presented overall and by treatment group.

Listings will be sorted by treatment group, subject ID, parameter (if applicable), and visit.

Continuous variables will be summarized using the following descriptive statistics: n (non-missing sample size), mean, standard deviation, median, maximum and minimum. All categorical measures will be summarized by the frequency and percentages (based on the non-missing sample size) of observed levels. The denominator for the percentages may be based on the number of non-missing observations for an assessment or based on the number of subjects in a population. This will be described for each table.

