14. TECHNICAL DETAILS

SAS version 9.4 or above will be used to generate all tables, figures and listings.

**15. SUMMARY OF CHANGES IN THE CONDUCT OF THE STUDY OR
PLANNED ANALYSES**

Not applicable.

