14.3 Safety Data

14.3.1 Displays of Adverse Events

Table 34: Overall Summary of Adverse Events*

	BPZE1 10 ⁷ CFU by VaxINator (N=X)		BPZE1 10 ⁹ CFU by VaxINator (N=X)		BPZE1 10 ⁹ CFU by Syringe (N=X)		Placebo by VaxINator (N=X)		All Subjects (N=X)	
	n	%	n	%	n	%	n	%	n	%
Subjects ^a with										
At least one local solicited adverse event	x	x	x	x	x	x	x	x	x	x
At least one systemic solicited adverse event	x	x	x	x	x	x	x	x	x	x
At least one unsolicited adverse event	x	x	x	x	x	x	x	x	x	x
At least one unsolicited non-serious adverse event through Day 29	x	x	x	x	x	x	x	x	x	x
At least one related unsolicited adverse event	x	x	x	x	x	x	x	x	x	x
Mild (Grade 1)	x	x	x	x	x	x	x	x	x	x
Moderate (Grade 2)	x	x	x	x	x	x	x	x	x	x
Severe (Grade 3)	x	x	x	x	x	x	x	x	x	x
Not yet assessed										
At least one severe (Grade 3) unsolicited adverse event	x	x	x	x	x	x	x	x	x	x
Related	x	x	x	x	x	x	x	x	x	x
Unrelated	x	x	x	x	x	x	x	x	x	x

Table 34: Overall Summary of Adverse Events *(continued)*

	BPZE1 10 ⁷ CFU by VaxINator (N=X)		BPZE1 10 ⁹ CFU by VaxINator (N=X)		BPZE1 10 ⁹ CFU by Syringe (N=X)		Placebo by VaxINator (N=X)		All Subjects (N=X)	
	n	%	n	%	n	%	n	%	n	%
Subjects ^a with										
At least one serious adverse event ^b	x	x	x	x	x	x	x	x	x	x
At least one related, serious adverse event	x	x	x	x	x	x	x	x	x	x
At least one adverse event leading to early termination ^c	x	x	x	x	x	x	x	x	x	x
At least one medically attended adverse event	x	x	x	x	x	x	x	x	x	x
At least one new onset chronic medical condition	x	x	x	x	x	x	x	x	x	x
At least one potentially immune mediated medical condition	x	x	x	x	x	x	x	x	x	x
N = Number of subjects in the Safety Population ^a Subjects are counted once for each category regardless of the number of events. ^b A listing of Serious Adverse Events is included in Table 56. ^c As reported on the Adverse Event eCRF.										

Table 35: Adverse Events Occurring in 5% of Subjects in Any Treatment Group by MedDRA System Organ Class and Preferred Term, and Treatment Group - Safety Population*

Preferred Term	MedDRA System Organ Class	BPZE1 10 ⁷ CFU by VaxINator (N=X)			BPZE1 10 ⁹ CFU by VaxINator (N=X)			BPZE1 10 ⁹ CFU by Syringe (N=X)			Placebo by VaxINator (N=X)			All Subjects (N=X)		
		n	%	Events	n	%	Events	n	%	Events	n	%	Events	n	%	Events
Serious Adverse Events																
All	All	x	x	x	x	x	x	x	x	x	x	x	x	x	x	x
PT1	SOC1	x	x	x	x	x	x	x	x	x	x	x	x	x	x	x
Etc.	Etc.															
Other (Non-serious) Adverse Events																
All	All	x	x	x	x	x	x	x	x	x	x	x	x	x	x	x

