14.3.1.1 Solicited Adverse Events

Table 36: Number and Percentage of Subjects Experiencing Solicited Events with 95% Confidence Intervals by Symptom and Treatment Group*

Symptom	BPZE1 10 ⁷ CFU by VaxINator (N=X)			BPZE1 10 ⁹ CFU by VaxINator (N=X)			BPZE1 10 ⁹ CFU by Syringe (N=X)			Placebo by VaxINator (N=X)			All Subjects (N=X)		
	n	%	95% CI	n	%	95% CI	n	%	95% CI	n	%	95% CI	n	%	95% CI
Any Symptom	x	xx	x x, x x	x	xx	x.x, x x	x	xx	x x, x.x	x	xx	x x, x.x	x	xx	x x, x.x
Any Systemic Symptom															
Fever															
Feverishness															
Fatigue (tiredness)															
Malaise (general unwell feeling)															
Myalgia (body aches /muscular pain)															
Arthralgia (joint pain)															
Headache															
Rash / hypersensitivity															
Any Local Symptom															
Runny nose															
Stuffy nose/congestion															
Nasal pain/ Irritation															
Epistaxis															
Sneezing															
Sinus pressure/pain															
Sore/irritated throat															
Cough															
Shortness of breath/wheezing															

Note: N= Number of subjects in the Safety Population

Table 37: Comparison of the Proportion of Subjects Experiencing Solicited Events by Treatment Group*

Symptom	Statistic	BPZE1 10 ⁷ CFU by VaxINator (N=X)	BPZE1 10 ⁹ CFU by VaxINator (N=X)	BPZE1 10 ⁹ CFU by Syringe (N=X)	Placebo by VaxINator (N=X)
Any Symptom	Proportion	x.xx	x.xx	x.xx	x xx
	95% CI (for proportion)	x xx, x.xx	x xx, x.xx	x xx, x.xx	x xx, x xx
	Difference ^a	x.xx	x.xx	N/A	N/A
	95% CI (for difference)	x xx, x.xx	x xx, x.xx	N/A	N/A
[Symptom 1]	Proportion	x.xx	x.xx	x.xx	x xx
	95% CI (for proportion)	x xx, x.xx	x xx, x.xx	x xx, x.xx	x xx, x xx
	Difference ^a	x.xx	x.xx	N/A	N/A
	95% CI (for difference)	x xx, x.xx	x xx, x.xx	N/A	N/A
Note: N = Number of subjects in the Safety Population who received at least one dose ^a vs. placebo					

Table 38: Number and Percentage of Subjects Experiencing Solicited Events by Symptom, Maximum Severity, and Treatment Group*

Symptom	Severity	BPZE1 10 ⁷ CFU by VaxINator (N=X)			BPZE1 10 ⁹ CFU by VaxINator (N=X)			BPZE1 10 ⁹ CFU by Syringe (N=X)			Placebo by VaxINator (N=X)			All Subjects (N=X)		
		n	%	95% CI	n	%	95% CI	n	%	95% CI	n	%	95% CI	n	%	95% CI
Any Symptom	None	x	xx	x.x, x x	x	xx	x x, x.x	x	xx	x.x, x x	x	xx	x x, x.x	x	xx	x x, x.x
	Mild															
	Moderate															
	Severe															
Systemic Symptoms																

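### The SAP omits the protocol's pooled BPZE1 10^9 CFU group, and its only pooled safety column includes placebo, so BPZE1 safety rates appear only arm by arm

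*SAP*

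**What the plan says.** Protocol 11.4 (Final Analysis Plan) defines the reporting groups: "All analyses will be presented by treatment group (i.e. group by BPZE1 10^9 CFU, BPZE1 10^7 CFU, or Placebo"). It then adds that the 10^9 results "will be further grouped by vaccination device (group by VaxINator or needleless tuberculin syringe) to allow for comparison of immunogenicity results" with the Phase 1 trials. The dose-level 10^9 group is therefore the stated default. The device split is an extra layer, and the reason given for it is immunogenicity.

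Protocol 11.4.2 (Safety Data) repeats the rule for safety: "All summaries and analyses will be presented by treatment group".

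SAP 6.1 (General Principles) sets a different layout: "All summary tables will be structured with a column for each treatment in the order" 10^7 by VaxINator, 10^9 by VaxINator, 10^9 by syringe, placebo. SAP 9 adds: "Safety summaries will be presented overall and by treatment group". In the shells the overall presentation is a column, or in the laboratory tables a row, headed *All Subjects*. Under Table 34 the denominator is given as "N = Number of subjects in the Safety Population", which includes placebo recipients. Tables 36, 38, 39 and 50 attach a 95% confidence interval to that column. Tables 44, 49 and 55 are whole tables for *All Subjects*.

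No shell has a combined 10^9 column. SAP 15, the section for changes to the planned analyses, reads as not applicable.

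**The concern.** Safety and tolerability form the primary objective, and both documents state that objective by dose (10^7 or 10^9 CFU), not by device. Protocol 11.4 says the results will inform the dose for Phase 2b. For the higher dose the SAP replaces one estimate on 20 subjects with two on 15 and 5, and does not record that it has done so.

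The pooled figure that the SAP does prespecify, with an interval in four tables, is a weighted average of vaccine and placebo whose weights are the allocation ratio. A reader looking for one summary safety rate will find that column first, and it is not a rate in vaccinated subjects.

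**Working it through.** **Inputs.** Planned sizes of 15, 15, 15 and 5 (Protocol 4, Table 2; SAP 4.4.3 and 5). Pooled 10^9 is 15 + 5 = 20. All BPZE1 is 15 + 15 + 5 = 35 of 50, or 70%; placebo is 15 of 50, or 30%.

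**The plan's own figures.** Protocol Table 3 and SAP Table 3 give the chance of seeing at least one event, 1 − (1 − p)^n.

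- n=15: 1 − 0.90^15 = 79.4% and 1 − 0.99^15 = 14.0%. Both match.
- n=5: 1 − 0.90^5 = 41.0% and 1 − 0.99^5 = 4.9%. Both match.
- The cell for n=15 at 0.01% computes to 0.15% but is printed as below 0.1. This does not affect the point.

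**The same formula for the protocol's pooled group, n=20.** 1 − 0.90^20 = 87.8% and 1 − 0.99^20 = 18.2%.

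**Exact two-sided 95% upper limit with no events**, 1 − 0.025^(1/n):

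| Group | n | Upper limit |
|---|---|---|
| 10^9 by syringe | 5 | 52.2% |
| 10^9 by VaxINator | 15 | 21.8% |
| 10^9 combined (Protocol 11.4) | 20 | 16.8% |
| All BPZE1 (in neither document) | 35 | 10.0% |

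**Exact 95% interval at an observed rate of 20%.** 1/5 gives 0.5% to 71.6%; 3/15 gives 4.3% to 48.1%; 4/20 gives 5.7% to 43.7%. Pooling narrows the interval from 43.8 percentage points (VaxINator arm) to 38.0.

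**What *All Subjects* estimates.** With the planned sizes, its expected value is 0.7 × (BPZE1 rate) + 0.3 × (placebo rate). The rates below are assumed, for illustration:

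| BPZE1 | Placebo | *All Subjects* |
|---|---|---|
| 10% | 0% | 7% |
| 20% | 0% | 14% |
| 40% | 20% | 34% |
| 40% | 40% | 40% |

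The column matches the BPZE1 rate only in the last row, where the two rates are equal.

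**The case against.** **The SAP's four columns can be defended.** Protocol 4 and 5.3.1 list four groups or arms, and Protocol 11.2 sizes safety detection at N=15 and N=5. On that view, reporting by treatment group simply means four columns. The protocol does use the term in both senses, but 11.4 spells out what it means for the analyses, and there 10^9 is one group.

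**A reader might infer that no table gives the safety rate in BPZE1 recipients.** The shells do not support that. Tables 34 to 36, 38, 39 and 50 give n and % for each of the three BPZE1 arms, several with intervals. Table 37 gives each arm's proportion and interval, and the difference from placebo for both VaxINator arms. Because n and N are printed, pooled proportions can be summed by hand. Only the prespecified pooled rate and its interval are absent.

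**A reader might also infer that *All Subjects* understates vaccine risk.** That holds only if the placebo rate is the lower one. Protocol 2.1.1 and 2.1.2 report no detectable differences in adverse events between placebo and dose groups in Phase 1. Nothing in the SAP uses the column as the vaccine's safety estimate, and Table 37, the between-arm comparison, does not contain it.

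**Nor does either document ask for an all-BPZE1 pool.** Such a pool averages doses 100-fold apart in a trial meant to inform dose.

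**Pooling the two devices has a real drawback.** Device is known (Protocol 5.3.2) and the syringe delivers only 10^9 BPZE1, so those five subjects can infer that they received vaccine. A combined column mixes their symptom reports with blinded ones. This objection stands. It is a reason to read the combined column beside the VaxINator arm, but not a reason to drop a protocol grouping without saying so.

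**Conclusion.** The SAP departs from Protocol 11.4 by omitting the combined 10^9 group and does not record the departure. Its only pooled safety column includes placebo.

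The size is moderate. The zero-event upper limit for the 10^9 dose would be 16.8% rather than 21.8% (VaxINator) and 52.2% (syringe), and the chance of seeing a 10% event would be 87.8% rather than 79.4% and 41.0%. These figures assume the planned arm sizes and, for the combined group, that the event rate does not differ by device. The size of the *All Subjects* dilution depends on the unknown placebo rate and is zero if the rates are equal.

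No primary result is invalidated and no data are lost. The defect is a missing prespecified estimate on the primary objective, next to a pooled column that is easily misread.

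**What to change.** 1. Add a *BPZE1 10^9 combined* column (planned N=20) with exact 95% intervals to SAP Tables 34, 35, 36, 38, 39 and 50. Tables 34 and 35 have no interval column at present, so one would have to be added there. Keep the four arm columns as primary.
2. Label *All Subjects* in those tables, in the laboratory tables and in Tables 44, 49 and 55 as a study total that includes placebo, not a vaccine safety rate.
3. Where the combined group is still not shown (the immunogenicity tables use the same four columns), record and justify that in SAP 15.
4. Optionally add an *All BPZE1* column (N=35), marked as a supplement that the protocol does not require.

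The cost is one further group in six tables that already have five, and some footnotes; no new data are needed. The wider tables are a nuisance, chiefly Table 50 with four sub-columns per group. The combined column mixes devices, and the syringe recipients' assignment is effectively known, so a footnote should direct the reader to the VaxINator-only arm beside it.

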6.2. Timing of Analyses

- The preliminary safety and immunogenicity analysis will be performed when all safety, reactogenicity, immunogenicity and *B. pertussis* colonization data through Day 46 (or Day 29 if no subjects remain colonized with *B. pertussis* at Day 29) are available.
- The final analysis will be performed after all clinical, safety, and reactogenicity data through approximately 180 days after the study vaccination are available. Once the last subject completes the last visit, the final clinical database will be cleaned, monitored and locked. Unblinded analyses of safety, reactogenicity, colonization, and available immunogenicity data will then be performed by the SDCC and will be included in the CSR.

6.3. Analysis Populations

Summaries and analysis of safety data will be presented for the Safety Population. Summaries and analysis of immunogenicity data will be presented for the Immunogenicity Population. If there are major protocol deviations, a per-protocol (PP) analysis may also be performed. Summaries and analysis of nasal colonization data will be presented for the PP Population. A tabular listing of all subjects, visits, and observations excluded from the analysis populations will be provided in the CSR ([Listing 4](#), [Appendix 16.2.3](#)).

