To minimize the risk of transmission, the volunteers will stay at the study center for 2 hours after administration of the vaccine. In addition, volunteers with household or professional contact with infants below one year of age or household/professional contact with individuals with immunodeficiency will be excluded from participation in the study. The attenuated BPZE1 bacteria colonize the upper respiratory tract similarly to wild-type *B. pertussis*. Colonization of live organism will be assessed from a nasopharyngeal swab performed 28 days after administration to ensure all subjects are cleared of colonization. If a subject is not clear at day 29, a repeat nasal swab and culture will be performed at day 46. Chronic carriage of BPZE1 has not been reported (i.e., the vast majority of subjects have been clear at day 29 and no subject has had positive cultures at day 46) and is therefore not expected. Any subject who remains positive at day 46 will be provided a short course of azithromycin, which is clinically used to eradicate *B. pertussis* from the nasopharynx. Azithromycin will be prescribed by a study physician and filled by the hospital pharmacy or the patient's desired pharmacy at no cost to the subject.

Furthermore, in animal studies, when female mice were vaccinated with BPZE1 shortly before mating, no negative effect on either the pregnancy or their offspring was observed. The offspring were protected against *B. pertussis* challenge, based on evaluation of the lungs at necropsy.[16]

[REDACTED]

2.3.1.3 Risks to the Environment or Potential for Interaction with wild-type *B. pertussis* strains

Detailed information about the [REDACTED] BPZE1 is available in the environment risk assessment located in the investigator's brochure.

To avoid accidental exposure to the environment and to study staff, actions should be taken to minimize generation of aerosols, since the bacteria are strictly respiratory tract organisms. Staff members should wear eye-protective glasses during the vaccination. Persons handling BPZE1 should wear gloves and must practice standard hand hygiene before touching their skin or eyes.

[REDACTED]

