6.3.3. Per Protocol Population

The Per Protocol (PP) Population will include all subjects in the immunogenicity population, with the following exclusions:

-
- Data from all available visits for subjects found to be ineligible at baseline.
 - Data from all visits subsequent to major protocol deviations, such as:
 - Receipt of non-study licensed live vaccine within 30 days before or after the study vaccination,
 - Receipt of non-study licensed inactivated vaccine within 14 days before or after the study vaccination,
 - Receipt of immunosuppressive therapy (e.g., corticosteroids) within 30 days before or after the study vaccination.
 - Data from any visit that occurs substantially out of window. Whether a visit that occurs substantially out of window will be determined jointly by the principal investigator, the Sponsor, and the SDCC.

For analyses using the PP population, subjects will be grouped based on study vaccinations received.

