Immune responses in terms of the ratio of toxin-specific (PT, FHA, PRN, FIM 2/3) nasal mucosal IgA antibody to total nasal mucosal IgA antibody will be summarized at each time point (Table 29 and Table 30.) Analyses will include the geometric mean titer ratios (GMTR) of antigen-specific IgA to total IgA and corresponding 95% confidence intervals, along with fold change of the GMTR from baseline. The proportion of subjects achieving seroconversion, defined as ≥ 2 -fold rise of the GMTR from baseline, to each antigen (PT, FHA, PRN, and FIM 2/3) will be reported (Table 29 and Table 30) as well as the proportion of subjects that achieve seroconversion by nasal aspirate ELISA to one or more (Table 31 and Table 32) antigens (PT, FHA, PRN, and FIM 2/3) at either or both of Day 29 and Day 181. Rates of seroconversion will be compared using Barnard's exact test. Reverse cumulative distributions (RCD) curves will also be presented for mucosal PT, FHA, PRN, and FIM 2/3 antibody titers. Plots for each assay will be generated with three panels (pre-vaccination, Day 15, Day 29, and Day 181), and separate curves within each panel for each treatment group, as shown in Figure 7 and Figure 8. Individual immunogenicity response data will also be presented (Listing 9.)

Subjects will be tested for *B. pertussis* colonization by culture at Day 29 and, if positive, again at Day 46. The proportion of subjects with positive *B. pertussis* culture will be reported for the PP population at each time point with corresponding 95% confidence intervals (Table 33.) Individual nasal colonization data will also be presented (Listing 13.)

No formal hypothesis testing is planned.

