^b 2-Fold Rise represents the percentage of subjects with at least a 2-Fold Rise in antibody compared to pre-dose 1.

^c vs. placebo

^dBarnard's Exact test

*Day 181 time point will not be presented in Preliminary Analysis

Tables with similar format:

Table 30: Mucosal IgA to Total IgA ELISA Geometric Mean Titer Ratio (GMTR) and Seroconversion (2-Fold Rise) Results by Time Point and Treatment Group, Per Protocol Population*

Table 31: Any One or More Mucosal Pertussis Antigens Seroconversion (2-Fold Rise) Results by Time Point and Treatment Group, Immunogenicity Population*

Time Point	Statistic	BPZE1 10 ⁷ CFU by VaxINator (N=X)	BPZE1 10 ⁹ CFU by VaxINator (N=X)	BPZE1 10 ⁹ CFU by Syringe (N=X)	Placebo by VaxINator (N=X)
Day 29 Post-Vaccination	N	x	x	x	x
	2-Fold Rise ^a	x x	x x	x x	x.x
	95% CI	x x, x x	x.x, x x	x.x, x x	x.x, x x
	Difference ^b	x x	x x	N/A	N/A
	95% CI of Difference	x x, x x	x.x, x x	N/A	N/A
	p-value ^c	0 xx	0 xx	N/A	N/A
Day 181 Post-Vaccination	N	x	x	x	x
	2-Fold Rise ^a	x x	x x	x x	x.x
	95% CI	x x, x x	x.x, x x	x.x, x x	x.x, x x
	Difference ^b	x x	x x	N/A	N/A
	95% CI of Difference	x x, x x	x.x, x x	N/A	N/A
	p-value ^c	0 xx	0 xx	N/A	N/A

Note: N=Number of subjects in the Immunogenicity Population
^a 2-Fold Rise represents the percentage of subjects with at least a 2-Fold Rise in one or more antibodies compared to pre-dose 1.
^b vs. placebo
^cBarnard's Exact test

*Day 181 time point will not be presented in Preliminary Analysis

Tables with similar format:

Table 32: Any One or More Mucosal Pertussis Antigens Seroconversion (2-Fold Rise) Results by Time Point and Treatment Group, Per Protocol Population*

Table 33: Nasal Colonization Results by Time Point and Treatment Group, Per Protocol Population*

Time Point	Statistic	BPZE1 10 ⁷ CFU by VaxINator (N=X)	BPZE1 10 ⁹ CFU by VaxINator (N=X)	BPZE1 10 ⁹ CFU by Syringe (N=X)	Placebo by VaxINator (N=X)
Day 29 Post-Vaccination	Subjects with detectable B. pertussis , n	x	x	x	x
	Proportion of subjects with detectable B. pertussis	xx	xx	xx	xx
	95% CI	x x, x x	x.x, x x	x x, x.x	x x, x x
Day 46 Post-Vaccination	Subjects with detectable B. pertussis , n	x	x	x	x
	Proportion of subjects with detectable B. pertussis	xx	xx	xx	xx
	95% CI	x x, x x	x.x, x x	x x, x.x	x x, x x

Note: N=Number of subjects in the Per Protocol Population

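### Colonisation by the live vaccine strain is tabulated only in the per-protocol population, and the Day 46 denominator is not defined

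*SAP*

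**What the plan says.** Both documents assign the colonisation summary to the per-protocol (PP) population. Protocol 11.4 says "colonization data will be summarized using per-protocol population", SAP 6.3 says "Summaries and analysis of nasal colonization data will be presented for the PP Population", and SAP 8.1 says that the proportion with a positive "culture will be reported for the PP population at each time point with corresponding 95% confidence intervals". Table 33 is the only table of these results and has no Safety or Immunogenicity version.

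The protocol puts the colonisation paragraph inside section 11.4.2 on safety data, which opens with "Summaries and analysis of safety data will be presented for the Safety Analysis Population". Section 2.3.1.2 gives the purpose of the swab as "to ensure all subjects are cleared of colonization". Colonisation data are also among the items for interim safety review (protocol 11.3.1, SAP 6.6.1).

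SAP 6.3.3 builds PP from the Immunogenicity Population. It removes all data of subjects found ineligible at baseline, visits after a major deviation, and visits judged substantially out of window. One listed deviation is "Receipt of immunosuppressive therapy (e.g., corticosteroids) within 30 days before or after the study vaccination".

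At Day 46 only subjects positive at Day 29 are cultured (SAP 4.5.3). On denominators, SAP 6.1 says "The frequency and percentages (based on the non-missing sample size) of observed levels will be reported for all categorical measures". The note under Table 33 says only "Note: N=Number of subjects in the Per Protocol Population".

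**The concern.** A question about whether all vaccinated subjects have stopped carrying a live organism is answered in a subset chosen for interpreting immune response. A positive culture remains valid evidence of carriage whether or not the subject later proves ineligible, takes a steroid course or attends late. A late positive culture in particular shows long carriage, yet the visit-window rule can remove it.

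The second difficulty is reading the Day 46 row. Under SAP 6.1 the percentage describes the few subjects re-cultured; under the Table 33 note it appears to describe the arm. With so few subjects the two readings can differ many-fold.

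Table 33 is marked for the preliminary report, which may be shared for planning subsequent trials. SAP Appendix 3 excludes listings from that report, so a carrier outside PP would not appear there in any form.

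**Working it through.** **The plan's own figure.** The documents state no expected Day 29 or Day 46 positive rate. The nearest stated figure is Table 3: the chance of at least one event in an arm of 15 is 1 − (1 − p)^15.
- p = 10%: 1 − 0.9^15 = 79.4%, as printed.
- p = 1%: 1 − 0.99^15 = 14.0%, as printed.
- With 14 subjects these become 77.1% and 13.1%.

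Losing one subject therefore costs little sensitivity. What matters is whether the lost subject is a carrier.

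**Effect of the population.** The counts are assumptions. The intervals are exact (Clopper-Pearson), also an assumption because no method is named for colonisation. For 0 of n the upper limit is 1 − 0.025^(1/n); for 1 of n the lower limit is 1 − 0.975^(1/n).

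| Arm | All vaccinated, one carrier | PP, carrier removed |
|---|---|---|
| VaxINator, 15 | 1/15 = 6.7% (0.2 to 31.9) | 0/14 = 0% (0 to 23.2) |
| Syringe, 5 | 1/5 = 20% (0.5 to 71.6) | 0/4 = 0% (0 to 60.2) |

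**Effect of the Day 46 denominator.** Take an arm of 15, all in PP, with one subject positive at Day 46.

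| Day 29 positives, all re-cultured | Denominator under SAP 6.1 | Denominator = PP N |
|---|---|---|
| 1 | 1/1 = 100% (2.5 to 100) | 1/15 = 6.7% (0.2 to 31.9) |
| 2 | 1/2 = 50% (1.3 to 98.7) | same |
| 3 | 1/3 = 33.3% (0.8 to 90.6) | same |
| 5 | 1/5 = 20% (0.5 to 71.6) | same |

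**Which denominator applies.** SAP 6.1 points to subjects with a Day 46 result. SAP 9 allows either the non-missing count or the population count for safety tables and promises to say which for each table; Table 33 does not. Tables 17, 21, 25 and 29 define n as subjects with results at the time point, whereas Table 33 uses n for the number positive and has no row for the number tested.

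**Direction of bias.** Slower clearance after immunosuppressive therapy is plausible, but neither document gives clearance data for such subjects. Other exclusions could act the opposite way. High baseline PT or pertactin IgG makes a subject ineligible (protocol 5.2). In Phase 1b the high-pertactin group had 33% colonisation, against (10 + 9 + 10)/(3 × 12) = 29/36 = 80.6% in the randomised vaccine groups (protocol 2.1, 2.1.2). Recent use of antibiotics active against the organism is also an exclusion. Removing subjects of these kinds would tend to raise the PP rate.

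**The case against.** The case for leaving the plan alone has several parts.

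- Colonisation is a secondary outcome, and the conditional Day 46 result is pre-specified in the outcome measures. Both are true. The conditional result should stay, but its denominator needs to be printed.
- Carriers are not hidden from the final report. Listing 13 gives each subject's culture result with no stated PP restriction, Listing 4 flags data removed from analysis, and the safety committee may see colonisation data. This holds for the clinical study report and the committee, but not for the preliminary report.
- PP is less restrictive than it may look. After pre-vaccination samples, a valid post-vaccination nasal result can qualify a subject without a post-vaccination serum result. Only visits after a deviation are dropped, so a steroid course after the Day 29 swab leaves that culture in. Only visits substantially out of window go. Immunosuppression and recent steroid use are already exclusions at entry. Few cultures may therefore be lost.
- Table 33 prints the number positive at Day 29 above the Day 46 rows, so a careful reader could work out the number due for testing. That does not show how many were actually tested or which denominator was used.
- Counting Day 29 negatives as negative at Day 46 may seem to conflict with the no-imputation rule in SAP 6.5. This is a fair caution, and it is why the convention needs a footnote and the conditional rate alongside.

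A reader might infer that PP removes the subjects most likely to stay positive and so biases the result towards clearance. The documents do not support this: they give no clearance data for the removed subjects, and some exclusions could act the other way. A reader might also infer that the SAP fixes Day 29 positives as the Day 46 denominator. It does not; that is the SAP 6.1 default, and the only count defined under Table 33 is a different one.

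**Conclusion.** The point holds in a limited form. A result the protocol handles as a safety matter is tabulated only in PP, and PP rules can discard valid cultures, positive ones included. One lost carrier changes an arm of 15 from 6.7% to 0%, although the intervals (0.2 to 31.9 and 0 to 23.2) overlap widely. The direction of any overall bias is unknown. The Day 46 denominator is undefined, and one positive could be shown as anything from 6.7% to 100%.

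The sizes rest on assumed counts and on exact intervals. Earlier studies reported no Day 46 positives (protocol 2.3.1.2), so the Day 46 problem may never arise. It should be settled beforehand because it would matter precisely when a carrier is found.

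**What to change.** In SAP 6.3 and 8.1, make the Safety Population with a culture result the main set for Table 33 and keep the PP version as supportive. Align protocol 11.4 and 11.4.2, or record the change in SAP section 15.

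In Table 33:
- add a row for the number tested at each time point;
- at Day 46, report positives among Day 29 positives tested, and positives over all subjects cultured at Day 29;
- footnote that Day 29 negatives were not re-cultured and are counted as negative in the second figure;
- name the confidence interval method.

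The cost is some SAP wording and one extra version of one table. No new data are needed and no study procedure changes.
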